This study is designed to evaluate a transdiagnostic CBT specifically constructed to treat Veterans with depressive/anxiety disorders. The protocol includes both a primary transdiagnostic exposure component as well as supplementary disorder-specific modules to address ancillary symptoms. This transdiagnostic CBT has been investigated through focus groups with Veterans and two pilot demonstrations. This study will compare transdiagnostic CBT to an existing evidence-based version of CBT, behavioral activation therapy (BAT; psychotherapy control condition). A randomized controlled trial (RCT) of 96 DVA patients with depressive/anxiety disorders will be conducted to examine its efficacy, feasibility, and accessibility. Diagnostic interviews and self-

report symptom questionnaires will be completed at pre-treatment, immediate post-treatment, and 6-month followup assessment time points.

Research Primary Aim 1: To examine efficacy of transdiagnostic CBT on reducing transdiagnostic and disorderspecific mental health symptoms and improving quality of life at immediate post-treatment and 6-month follow-up. Hypothesis 1: The transdiagnostic CBT will result in significantly greater reductions in symptomatology (for principal and comorbid diagnoses) and improvements in quality of life compared to the BAT control condition at immediate post-treatment and 6-month follow-up. Although limited specific symptoms may ultimately be comparable across treatments (e.g., depression), the transdiagnostic CBT will demonstrate significantly greater reductions in the majority of symptoms (e.g., anxiety, panic, fear, stress).

Research Primary Aim 2: To examine feasibility and acceptability of transdiagnostic CBT

Hypothesis 2: The transdiagnostic CBT will be well tolerated by DVA patients as demonstrated by improved attendance and dropout rates, patient satisfaction questionnaires, and positive feedback in post-treatment patient interviews as compared to the BAT control condition. This hypothesis is based on the predicted greater symptom improvement (hypothesis 1) as well as the flexibility and individual tailoring of the treatment approach incorporated within transdiagnostic CBT.

B. BACKGROUND AND SIGNIFICANCE

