RCT of Transdiagnostic CBT

Objective

To evaluate the transdiagnostic CBT in a RCT of VAMC patients with depressive/anxiety disorders by investigating its preliminary efficacy in reducing symptomatology, comorbidity, and improving quality of life compared to BAT (psychotherapy control condition) at immediate post-treatment and 6-month follow-up. Patient satisfaction and predictors of feasibility (attendance and dropout) also will be assessed.

Recruitment Strategy

VAMC patients will be recruited through the Primary Care – Mental Health Integration program and CBT Clinic at the RHJ VAMC. Within these programs, all VAMC patients reporting symptoms of depression and anxiety meet with a mental health staff member to complete a diagnostic interview and self-report measures as part of their standard clinical practices. If VAMC patients endorse symptoms consistent with a depressive/anxiety disorder, the patient's interest in participating in research will be assessed and, if agreeable to research, patients will be put in contact with research staff (same day meeting and/or follow-up phone to schedule research assessment). A research assessment will be completed with the project staff to first complete consent documentation and then assess inclusion/exclusion criteria (with a targeted sample of 96 VAMC patients; \geq 72 completers), including a semi-structured clinical interview and self-report questionnaires focused on the psychiatric symptoms and quality of life (described later). Participants who meet diagnostic criteria for the targeted disorders will be randomized into a study condition, and will be assigned to a project therapist. Because most VAMC patients who meet study criteria likely will present with multiple depressive/anxiety disorders, principal diagnosis, or the most impairing of

the diagnosable disorders, will be used to select patients for participation. To balance diagnoses across the two conditions, a stratified random assignment based on principal diagnosis will be used for the most common principal diagnoses (MDD, PTSD, and PD). Based on new patient consults at the RJH VAMC (i.e., nearly 1000 in 2011 with at least one-half presenting with symptoms of an depressive/anxiety disorder), it is expected that \geq 50% of the recruited VAMC patients will have served in OEF/OIF and \geq 33% will be representative of minority groups.

Eligibility Criteria

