~33	6-Month Follow-Up Assessment	Clinical interview, immediate treatment interview, & self-report battery (7 measures), treatment satisfaction

Note. Behavior therapy involves the introduction, teaching, in-session and between-session practice, and mastery of behavioral therapeutic techniques designed to improve symptoms of depression and anxiety, including behavioral activation (BAT group) as well as situational, physical, thought, and emotional exposures (transdiagnostic CBT group). Final treatment session will take place between sessions 12-16, as determined by provider and participants' collective decision. Final treatment session will involve relapse prevention content. Post-treatment assessment will be completed 1 week immediately after final treatment session. 6-month follow-up assessment will be completed 6-months after final treatment session.

Randomization Procedures

Participants will be randomly assigned (1:1) to one of the two study arms (*n* = 48 per arm) using a permuted block randomization procedure. Randomization will be stratified by principal diagnostic group and block size will be varied to minimize the likelihood of unmasking. After determining eligibility and completing consent and baseline assessment materials, enrolled participants will be assigned to treatment groups by the Project Research Assistant using a computer generated randomization scheme. Once a participant is randomized and attends the first session, they will be included in the intent-to-treat analysis. Randomization will occur at the participant level. As such, we will take the following steps to minimize contamination between the two arms of the study: 1) only one member of a household will be eligible for enrollment; and 2) other VAMC providers will be informed of their patients' participation in the study, but will be blinded to the treatment condition of their patients.

Transdiagnostic CBT Treatment Condition

As noted above in the Preliminary Studies section, a transdiagnostic CBT protocol was developed and revised through two demonstration studies and one focus group. The resulting protocol involves several primary components, including psychoeducation on the symptoms of depression and anxiety (session 1), assessment of motivation and setup of treatment plans (session 2), exposure therapy (sessions 3-15), and relapse prevention (final session). In addition to these primary components, optional modules are included to supplement exposure

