The full intent to treat (ITT) analysis set will comprise all randomized participants. Missing data in the full analysis set will occur if participants drop out prior to the end of the study. Participants will not be discontinued from the study because of non-adherence and all will remain in the study unless consent is withdrawn or if there are concerns regarding participant safety. Missing data for the ITT analysis set will be imputed using multiple imputation methods. The results of analyses using study completers and protocol adherers (completer and perprotocol analyses) will be compared with results using the ITT analysis set to test sensitivity of study conclusions to study drop-outs and protocol non-adherence. In addition, the information on dropout proportion will be used as one of the outcome measures of intervention feasibility.

Efficacy (Symptomatology & Quality of Life) Measures Analyses (Primary Aim 1)

The continuous measures of intervention efficacy and quality of life are APPQ, DASS, IIRS, MASA, PCL, STICSA, and V/SF-36. The primary outcome time point is at the end of the active intervention phase (immediate post-treatment) and the secondary time point is at the end of the naturalistic 6-month follow-up period. The difference in mean change from baseline to end-of-active intervention (effect sizes) for transdiagnostic CBT versus BAT control condition will be estimated via 95% CI. For the secondary time-point analyses, transdiagnostic CBT versus BAT control differences in change from immediate end-of-intervention to the 6-month follow-up will also be estimated using 95% CI. By assessing the magnitude of the between-intervention-group differences, as described by the CI, clinicians can judge whether the novel intervention provides sufficient improvement in these outcomes to suggest a clinically significant result that warrants further investigation.

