In preliminary hypothesis testing, efficacy outcome variables will be compared using the generalized linear mixed models (GLMM) approach. This approach provides a general framework that accommodates a wide range of data types (continuous, ordinal, dichotomous, categorical, count) and distributional assumptions (e.g. Gaussian, Binomial, Poisson) and accommodates repeated measures, covariate structure among repeated observations, and missing data. In the first set of primary hypothesis testing analyses, immediate post-treatment scores for each outcome of interest will be used (separately) as the dependent variable in the model, intervention (transdiagnostic CBT versus BAT control) will be included as the primary independent variable, and pre-treatment scores for the outcome of interest will be added as covariates. When approximate normality is assumed, GLMM reduces to a general linear models (GLM) approach which, in the simplest case (intervention as the primary independent variable with baseline level of outcome variable as covariate), is equivalent to a comparison of change from baseline scores for transdiagnostic CBT versus BAT control using an independent sample t-test. Additional covariates (e.g. age, number of psychiatric comorbidities, race, sex, combat theatre, and number of treatment sessions) will be added to the model to adjust for putative confounding variables. If intervention differences in other baseline variables are found in initial descriptive analyses, these variables will be also be added to the multivariable model. In secondary analyses, the modeling procedure will be repeated for the period between immediate post-treatment and 6-month follow-up. Given that we are seeking preliminary evidence of treatment

efficacy (to justify the next step in this line of research), there will be no adjustment for multiple outcomes or time points to avoid an overly conservative approach at this preliminary stage.

Feasibility and Acceptability Analyses (Primary Aim 2)

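### The 6-month analysis is defined only as change since post-treatment, so the 6-month part of Hypothesis 1 has no prespecified CBT-versus-BAT estimate, CI or test relative to pre-treatment

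*Combined protocol and SAP*

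**What the plan says.** Two places set the target. Hypothesis 1 (Section A, Specific Aims) predicts greater symptom reduction and "improvements in quality of life compared to the BAT control condition at immediate post-treatment and 6-month follow-up". The trial objective (Section D, RCT of Transdiagnostic CBT) likewise refers to "improving quality of life compared to BAT (psychotherapy control condition) at immediate post-treatment and 6-month follow-up".

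The analysis is in Section D, Efficacy Measures Analyses (Primary Aim 1). Post-treatment is the primary time point and the end of the 6-month follow-up is the secondary one. At post-treatment, the between-arm difference in mean change from baseline gets a 95% CI, and the model takes the post-treatment score as outcome with the pre-treatment score as covariate. At 6 months the estimate is different: "transdiagnostic CBT versus BAT control differences in change from immediate end-of-intervention to the 6-month follow-up will also be estimated using 95% CI". For the test, "the modeling procedure will be repeated for the period between immediate post-treatment and 6-month follow-up", with neither outcome nor covariate named. The plan describes the simplest case of its model as one that "is equivalent to a comparison of change from baseline scores for transdiagnostic CBT versus BAT control using an independent sample t-test". It also says that from these intervals "clinicians can judge whether the novel intervention provides sufficient improvement in these outcomes to suggest a clinically significant result".

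The exploratory diagnostic-group analyses reuse the same models. No section gives a 6-month comparison anchored at pre-treatment.

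**The concern.** The hypothesis asks whether patients given CBT are better off than patients given BAT six months after treatment. The planned contrast asks whether the gap between arms widened or narrowed after treatment ended. Both are reasonable questions, but only the first is the one that Hypothesis 1 poses.

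The difference shows in the outcomes the investigators would most want to detect. If the benefit is fully durable, the planned 6-month interval centres on zero and can be read as no difference. If it partly fades, the interval leans towards BAT while CBT is still ahead. The plan invites clinicians to judge sufficiency of improvement from these intervals in order to decide on further investigation, so a durable effect could be under-reported.

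If the gap is left open, someone must choose a 6-month contrast after seeing the data, across seven instruments with no multiplicity adjustment.

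**Working it through.** **What each analysis estimates.** Let D1 and D6 be the true CBT-minus-BAT differences at post-treatment and at 6 months, signed so that positive favours CBT. Randomisation makes the expected pre-treatment difference zero.

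- Change from post-treatment to 6 months (the stated CI): D6 − D1.
- Repeated model, read through the plan's own equivalence with a change-score comparison: again D6 − D1.
- Repeated model with the post-treatment score as covariate (the natural but unstated reading): D6 − b·D1, where b is the within-arm slope of the 6-month score on the post-treatment score. This also conditions on a variable that treatment has already affected.
- 6-month score adjusted for the pre-treatment score: D6.

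This step needs no assumed value.

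**Can D6 be recovered?** The sum (baseline to post) + (post to 6 months) is the baseline-to-6-month change, so the two planned point estimates add up to an estimate of D6 if they come from the same imputed data. The interval also needs their covariance: Var(sum) = Var(first) + Var(second) + 2·Cov. The plan does not specify this step.

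**Illustration of size.** The documents give no between-arm effect and no correlation with the 6-month scores, and there is no stated figure to reproduce. Inputs:

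- n per arm: 48 randomised (Randomization Procedures), or 36 if the 72 targeted completers (Recruitment Strategy) split evenly, 72/2.
- Assumed: SD 1 at each visit, so b equals the correlation; D1 = 0.58; post-to-6-month correlation r = 0.6; pre-to-6-month correlation 0.4; two-sided 5%. The 0.58 is close to what 48 per arm can detect with 80% power without adjustment: (1.96 + 0.84)·√(2/48) = 0.57.

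CI half-width of the change contrast = t(0.975, 2n−2)·√(2(1−r)·2/n):

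- n = 36: 1.994·√(0.8·2/36) = 1.994·0.211 = 0.42.
- n = 48: 1.986·√(0.8·2/48) = 1.986·0.183 = 0.36.

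Rejection rates below use the noncentral t distribution for the change contrast and simulation for the two covariate-adjusted models. Ranges run from 36 to 48 per arm.

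| True 6-month benefit | Analysis | Expected value (SD) | Significant result |
|---|---|---|---|
| Fully kept, D6 = 0.58 | Change from post | 0.58 − 0.58 = 0 | 5% (2.5% each way) |
| | Adjusted for post | 0.58 − 0.6·0.58 = 0.23 | 21% to 27% for CBT |
| | Adjusted for pre | 0.58 | 75% to 86% for CBT |
| Half kept, D6 = 0.29 | Change from post | 0.29 − 0.58 = −0.29 | 27% to 35% for BAT |
| | Adjusted for post | 0.29 − 0.6·0.58 = −0.06 | about 5% for BAT |
| | Adjusted for pre | 0.29 | 26% to 34% for CBT |

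**Range.** With D1 from 0.4 to 0.6, post-to-6-month r from 0.5 to 0.8 and pre-to-6-month r from 0.3 to 0.5:

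- Fully kept: the change contrast stays at 5%; adjusted for post, roughly 8% to 35%; adjusted for pre, roughly 41% to 92%.
- Half kept: the change contrast is significant for BAT in roughly 13% to 63% of trials, and the post-adjusted model in roughly 2% to 28%; power adjusted for pre is roughly 14% to 38%.
- Half-width of the change contrast: 0.26 to 0.47 SD.

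The simulated extremes are good to about two percentage points.

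**The case against.** Four points deserve weight.

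**The model sentence is open, not wrong.** The procedure to be repeated uses pre-treatment scores as covariates, and the framework is said to handle repeated measures. One could read it as the 6-month score adjusted for pre-treatment, which does give D6. The plan's statement that baseline adjustment equals a change-score t-test is also loose: it is exact only if the covariate slope is 1, so it is weak evidence of what the repeated model will be. This stands in part. For the test, the fair charge is that the contrast is unspecified. The pre-treatment reading, though, is not stated and sits badly with the explicit change definition given for the CI.

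**Maintenance is a legitimate question.** Describing baseline to post and then post to 6 months is coherent, and a reader with both intervals is unlikely to be badly misled. That stands, and is why the contrast should be kept. It still provides no interval or test for the effect that Hypothesis 1 names.

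**The time point is secondary and the trial preliminary.** True. This limits the severity, but durability bears on the stated purpose of justifying the next study.

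**The illustrative figures rest on assumptions.** Also true. The algebra carries the point; the figures only show that the gap can be large.

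**Conclusion.** The concern holds. The 6-month CI is defined as D6 − D1, the 6-month model names neither outcome nor covariate, and nothing in the plan prespecifies a CBT-versus-BAT estimate, CI or test at 6 months relative to pre-treatment. Followed as written, the CI rule centres on zero for a fully maintained benefit and leans towards BAT for a partly faded one, whatever the effect size or correlation.

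The rejection rates depend on the assumed effect, correlations and numbers analysed, and should be read as illustration. The gap is one of prespecification: the data will be collected, the point estimate can be recovered, and the primary post-treatment analysis is unaffected. It should be fixed before outcome data are analysed by arm, but it does not threaten the trial's main result.

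**What to change.** In Efficacy Measures Analyses (Primary Aim 1):

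- Define the 6-month effect as the between-arm difference in the 6-month score adjusted for the pre-treatment score, with 95% CI and test. Use either ANCOVA or one repeated-measures model of the post-treatment and 6-month scores with an arm-by-visit term.
- State the outcome and covariate of the model that is to be repeated for the follow-up period.
- Keep the change from post-treatment to 6 months, labelled as a maintenance analysis.

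This costs one or two sentences, with no new data, visits or patients.

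Separately, and minor: the procedures table puts the follow-up visit at about week 33, while its note says that the "6-month follow-up assessment will be completed 6-months after final treatment session". Week 33 is 33 − 17 = 16 weeks after a session-16 finish and 33 − 13 = 20 weeks after a session-12 finish, both short of six months (about 26 weeks). The two entries must be reconciled so that the time point being analysed is clear.

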participants referred to this clinic already have expressed interest in receiving psychotherapy; and, thus, none of the 15 invited participants refused to participate in treatment. All participants were diagnosed with multiple comorbid depressive/anxiety disorders and reported severe, pre-treatment symptoms of anxiety and depression. PTSD was the most common presenting problem (46.6% PTSD, 26.7% SOC, 26.7% PD, 7.1%) and MDD was the most common comorbid disorder (64.2% MDD, 14.3% SOC, 7.1% PTSD, 7.1% PD). In general, participants were stabilized on multiple psychotropic medications prior to beginning CBT. Twelve of the fifteen participants finished treatment (80.0%). Treatment completers attended an average of 11.5, 50-minute sessions. As presented in the table below, participants demonstrated significant improvements in symptoms of impairment/quality of life, depression, stress, anxiety, and PTSD across all disorders and comorbidities. These findings provide preliminary support for the feasibility of a structured, transdiagnostic CBT protocol for the depressive/anxiety disorders among VAMC patients.

Scale (n)	Pre	Post	t (p)	Effect Size
IIRS-Impairment (12)	66.0 (14.9)	41.2 (19.8)	6.4 (< .001)	1.42
PTSD Checklist (7)	56.1 (13.1)	37.0 (14.0)	5.6 (< .01)	1.41
DASS-Depression (12)	26.2 (10.8)	10.3 (10.3)	5.3 (< .001)	1.51
DASS-Anxiety (12)	25.2 (10.7)	11.8 (9.1)	5.5 (< .001)	1.35
DASS-Stress (12)	26.3 (10.8)	15.7 (9.6)	3.6 (< .01)	1.04

Efficacy of Initial Transdiagnostic CBT in VAMC Patients

Note. Sum scores reported as means (standard deviations). Cohen's ds used for effect sizes.

Focus Group with OEF/OIF Veterans

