The results from the initial demonstration and OEF/OIEF Veteran focus groups were used to inform the revisions of the transdiagnostic CBT protocol. Once the revised protocol was complete, a demonstration of the revised transdiagnostic CBT protocol was initiated, once again, within standard clinical psychotherapeutic practices at the VAMC. The methods of the second demonstration were largely identical to the first demonstration. Thirty-one VAMC patients were recruited to complete the treatment. All participants were diagnosed with multiple comorbid depressive/anxiety disorders and reported severe pre-treatment symptoms. Among the twenty-three treatment completers, PTSD was the most common principal diagnoses (39.1% PTSD, 26.1% MDD, 21.7% PD, 8.7% SOC, and 4.3% OCD) and MDD was the most common comorbidity (43.5% MDD, 26.1% PTSD, 8.7% drug/alcohol abuse, 4.3% PD, 4.3% SOC). Treatment completers attended an average of 11.8, 45-60 minute sessions. As presented in the table below, participants demonstrated significant improvements in symptoms of impairment/quality of life, depression, stress, anxiety, and PTSD across all disorders and comorbidities. These findings provide additional support for the feasibility and likely efficacy of the transdiagnostic CBT protocol for the depressive/anxiety disorders among VAMC patients.

Efficacy of Revised Transdiagnostic CBT in VAMC Patients

Scale (n)	Pre	Post	t (p)	Effect Size
IIRS-Impairment (23)	64.3 (13.1)	37.3 (17.6)	7.3 (<.001)	1.74
PTSD Checklist (22)	56.5 (17.8)	33.7 (14.2)	7.2 (< .001)	1.42
DASS-Depression (23)	12.0 (6.1)	4.8 (4.3)	6.7 (< .001)	1.36
DASS-Anxiety (23)	10.9 (5.4)	5.0 (3.5)	6.2 (< .001)	1.30
DASS-Stress (23)	13.8 (5.1)	7.0 (3.9)	6.1 (< .001)	1.50

Note. Sum scores reported as means (standard deviations). Cohen's ds used for effect sizes.

D. RESEARCH DESIGN AND METHODS

Project Timeline

Project Component	Year	Timeframe
Preparing for RCT	Y01	month 01 – 06
Hiring staff	Y01	month 01 – 03
Training on procedures/protocols	Y01	month 03 – 06
Advertising upcoming trial for recruitment	Y01	month 03 – 06
Randomized controlled trial	Y01-Y04	month 06 – 54
Recruitment and active treatment		month 06 – 45
Ongoing data entry and integrity/fidelity review	VS	month 09 – 42
Data analyses of post-treatment (follow-up)		month 24 – 54
Grant application(s) (e.g., DVA CSR&D Merit)	Y04-Y05	month 36 – 60
Dissemination of findings	Y05	month 54 – 60
Revision of manual based on findings/feedback	Y05	month 54 – 60

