Eligible VAMC patients will be randomized into one of two treatment conditions: transdiagnostic CBT or an existing evidence-based version of CBT (BAT). Both treatment conditions will include 12-16 weekly 45-60-minute individual psychotherapy sessions. The total number of sessions will vary slightly depending on participant needs and progress during therapy, as is common in most CBT approaches to psychotherapy (and will serve as a covariate in the outcome analyses). The general format of sessions will involve: 1) brief check-in; 2) review of materials from previous sessions; 3) review of homework assignments; 4) overview of new materials and insession exercises; and 5) assignment of homework for next session. Attendance and homework completion will be recorded. A full battery of self-report questionnaires and a diagnostic interview will be completed pretreatment, post-treatment, and at the 6-month follow-up to track participants' progression through treatment and maintenance. Post-treatment participant interviews will be completed at immediate post-treatment and 6-month follow-up to collect feedback on participants' perspectives on the treatments.

Table of Procedures for Each Visit – Summarized Across Treatment Conditions

Week	Content	Assessment Summary
1	Pre-Treatment Assessment	Clinical interview & self-report battery (7 measures)
2	Session 1: Psychoeducation	Brief self-report battery (3 measures)
3 4 5	Session 2: Treatment planning Session 3: Introduction to behavior therapy Session 4: Behavior therapy	Brief self-report battery (3 measures)
6	Session 5: Behavior therapy	Brief self-report battery (3 measures)
7 8	Session 6: Behavior therapy Session 7: Behavior therapy	Brief self-report battery (3 measures)
9 10 11	Session 8: Behavior therapy Session 9: Behavior therapy Session 10: Behavior therapy	Brief self-report battery (3 measures)
12 13	Session 11: Behavior therapy Session 12: Behavior therapy	Brief self-report battery (3 measures)
14	Session 13: Behavior therapy (as needed)	Brief self-report battery (3 measures)
15 16 17	Session 14: Behavior therapy (as needed) Session 15: Behavior therapy (as needed) Session 16: Relapse prevention (as needed)	Brief self-report battery (3 measures)
~18	Post-Treatment Assessment	Clinical interview, immediate treatment interview, & self-report battery (7 measures), treatment satisfaction

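### The baseline-adjusted model is not equivalent to a t-test on change, and the plan does not say which of the two supplies the 95% CI that clinicians will judge

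*Combined protocol and SAP*

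**What the plan says.** Section D, Efficacy Measures Analyses (Primary Aim 1), describes two things for each outcome at immediate post-treatment.

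- **An estimate with a 95% CI.** The quantity is "The difference in mean change from baseline to end-of-active intervention (effect sizes"), compared between arms. No baseline adjustment is mentioned. This interval is the stated decision tool: "as described by the CI, clinicians can judge whether the novel intervention provides sufficient improvement in these outcomes".
- **A hypothesis test.** The post-treatment score is the dependent variable, arm is the main independent variable, and "pre-treatment scores for the outcome of interest will be added as covariates". In its simplest form, with arm and baseline score only, this model is said to be one that "is equivalent to a comparison of change from baseline scores for transdiagnostic CBT versus BAT control using an independent sample t-test".

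The section continues: "Additional covariates (e.g. age, number of psychiatric comorbidities, race, sex, combat theatre, and number of treatment sessions) will be added to the model". The Procedures section says of the session count: "The total number of sessions will vary slightly depending on participant needs and progress during therapy".

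**The concern.** A model with arm and pre-treatment score estimates the baseline slope from the data. A t-test on change fixes that slope at 1. They are different estimators with different standard errors. The approximate-normality condition attached to the sentence does not make them equal, and because the sentence keeps the baseline covariate in the model, it cannot be read as describing a model without one.

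The CI is described as a difference in mean change and the plan calls the two methods equivalent. An analyst could therefore report the CI from a change-score t-test and the p-value from ANCOVA. For one outcome the CI and the test could then disagree, and the interval meant to show whether further study is warranted could be wider than the same data allow.

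**Working it through.** **Why the two differ.** Let X be the pre-treatment score, Y the post-treatment score and b the baseline slope.

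- ANCOVA estimate: (difference in mean Y) − b × (difference in mean X), with residual variance SDpost²(1 − r²).
- Change-score estimate: (difference in mean Y) − 1 × (difference in mean X), with variance SDpre² + SDpost² − 2·r·SDpre·SDpost.
- Since b = r·SDpost/SDpre, the second variance equals SDpost²(1 − r²) + SDpre²(1 − b)². The excess is zero only at b = 1.

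**Inputs.** The tables headed "Efficacy of Initial Transdiagnostic CBT in VAMC Patients" and "Efficacy of Revised Transdiagnostic CBT in VAMC Patients" in section C give n, pre and post means and SDs, and t for five scales each. I take t as the paired statistic.

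**Reproducing the plan's own figures.** d = mean change / √[(SDpre² + SDpost²)/2]. For first-pilot IIRS this is 24.8/17.52 = 1.42; for revised-pilot DASS-Anxiety, 5.9/4.55 = 1.30. All ten stated values of d reproduce to two decimals, so the SDs can be read as raw SDs.

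**Formulas.**

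1. SDchange = mean change × √n / t
2. r = (SDpre² + SDpost² − SDchange²) / (2·SDpre·SDpost)
3. b = r·SDpost/SDpre
4. ANCOVA residual SD = SDpost·√(1 − r²)
5. CI width ratio = SDchange / residual SD

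**The two extreme rows.**

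- First-pilot IIRS: SDchange = 24.8 × √12/6.4 = 13.42; r = (14.9² + 19.8² − 13.42²)/(2 × 14.9 × 19.8) = 0.735; b = 0.98; residual SD = 13.42; ratio 1.000.
- Revised-pilot DASS-Anxiety: SDchange = 5.9 × √23/6.2 = 4.56; r = (5.4² + 3.5² − 4.56²)/(2 × 5.4 × 3.5) = 0.544; b = 0.35; residual SD = 2.94; ratio 1.555 (from unrounded values).

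**All ten rows.**

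| Row | n | r | Slope b | Width ratio | Change-score CI wider by |
|---|---|---|---|---|---|
| First pilot, IIRS | 12 | 0.74 | 0.98 | 1.000 | 0% |
| First pilot, PCL | 7 | 0.78 | 0.83 | 1.030 | 3% |
| First pilot, DASS-Depression | 12 | 0.52 | 0.49 | 1.178 | 18% |
| First pilot, DASS-Anxiety | 12 | 0.65 | 0.55 | 1.217 | 22% |
| First pilot, DASS-Stress | 12 | 0.51 | 0.45 | 1.231 | 23% |
| Revised pilot, IIRS | 23 | 0.36 | 0.49 | 1.081 | 8% |
| Revised pilot, PCL | 22 | 0.59 | 0.47 | 1.295 | 30% |
| Revised pilot, DASS-Depression | 23 | 0.56 | 0.39 | 1.441 | 44% |
| Revised pilot, DASS-Anxiety | 23 | 0.54 | 0.35 | 1.555 | 55% |
| Revised pilot, DASS-Stress | 23 | 0.32 | 0.24 | 1.446 | 45% |

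The median ratio is 1.224.

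**Sensitivity.**

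- *Equal pre and post SDs, same r:* the ratio is √[2/(1 + r)], which gives 1.06 to 1.23, median 1.14.
- *Lost degree of freedom:* with t quantiles at 48 per arm, the range is −0.5% to 54.6%.
- *Rounding:* rounding of t alone moves any ratio by less than 0.01. Rounding of all table entries together moves the top row between about 52% and 59%.

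**Disagreement between CI and test.** I simulated bivariate normal data with the pilot SDs and correlations, 48 per arm, 20,000 trials per row, two-sided 5%. The share of trials in which the two methods gave different p<0.05 verdicts was as follows. The effect sizes are assumptions, because the documents give no between-arm effect.

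| True effect (post-treatment SDs) | Range over the ten rows |
|---|---|
| 0 | 1% to 7% |
| 0.3 | 3% to 29% |
| 0.5 | 1% to 40% (median 20%) |
| 0.8 | 0% to 18% |

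In the revised-pilot DASS-Anxiety row at 0.5 SD, power is 46% for the change-score t-test and 82% for ANCOVA. Both methods held about 5% type I error.

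**The case against.** The strongest reply is that nothing in the plan tells anyone to run a t-test. The equivalence clause is explanatory and limited to the simplest case; the model actually prescribed is ANCOVA with further covariates. A difference in mean change is a quantity, not a method, and ANCOVA on change gives exactly the same arm effect as ANCOVA on the post-treatment score. The two paragraphs can therefore be read as compatible. This stands as far as it goes: the adjusted model could supply the CI, and the loss is conditional on its not doing so. But the plan does not settle the matter, and its one statement on the point says that the choice makes no difference.

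The size is also open to challenge. Six of the ten rows are DASS subscales from the same patients. The four IIRS and PCL rows give 0%, 3%, 8% and 30% (median about 6%). The 44% to 55% rows come from revised-pilot completers whose post SD fell well below the pre SD, which may not recur. Sampling error at n = 7 to 23 is large: a parametric bootstrap for the first-pilot PCL and DASS rows gives 95% ranges for the ratio from about 1.0 up to 1.9 to 2.1. All this stands. It makes the size uncertain, but it does not make the equivalence true.

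The 6-month CI has the same unstated adjustment. That contrast, however, starts from the post-treatment score, which is itself measured after randomisation, so the same adjustment should not simply be carried over. It needs its own treatment.

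**Conclusion.** The concern holds. The equivalence is false unless the baseline slope is 1, and the pilots imply slopes of 0.24 to 0.98. The plan also leaves open whether the CI for clinical judgement is baseline-adjusted. If it is not, the pilots imply intervals 0% to 55% wider than the same data allow (median 22%), or 6% to 23% (median 14%) with equal pre and post SDs, and verdicts that can differ from the reported test.

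These sizes assume that the pilot SDs and correlations apply in both arms. The pilots were single-arm completers. No BAT-arm SDs are given, four of the seven efficacy measures (APPQ, MASA, STICSA, V/SF-36) have no pilot data, and the trial analysis is intention-to-treat with multiple imputation. The trial's own ratio may differ.

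This is not a validity failure: both estimators are unbiased under randomisation and the hypothesis test is already adjusted. It should be corrected because the false statement sits in the primary efficacy analysis and the correction is almost free.

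**What to change.** - Delete the equivalence sentence.
- State that, for each outcome at immediate post-treatment, the effect estimate and its 95% CI are the baseline-adjusted mean difference from the model with arm and pre-treatment score, plus any prespecified baseline covariates, and that the test comes from the same model.
- Keep number of treatment sessions, and any other variable arising after randomisation, out of that model. The session count depends on progress during therapy, so treatment may affect it, and adjusting for it would no longer give a clean treatment contrast.
- Show unadjusted mean change by arm descriptively only.

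The cost is SAP wording and about one degree of freedom for the baseline term, which the plan's own test model already spends. In the least favourable pilot row (first-pilot IIRS, slope 0.98), the ANCOVA interval would be about 0.5% wider than the change-score interval at 48 per arm.
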